1. INTRODUCTION

1.1 BACKGROUND

Neonatal Encephalopathy and therapeutic hypothermia

Birth asphyxia related brain injury (hypoxic ischemic encephalopathy; HIE) occurs in 2.6 (95% CI 2.5 to 2.8) per 1000 live births in the UK, and is the most common cause of death and neurodisability in term babies^{1,2}. The economic burden to the treasury on support costs of neurodisability from HIE is massive (£4 billion per year). In addition, birth asphyxia related (obstetric) claims accounted for almost half of the NHS litigation expenses in 2016/17 (approx. £2 billion), increasing by 15% from the previous year. It has been reported that the NHS cost to meet the complex life-long care needs of babies born with brain damage could be soon over £20m per child, and this situation is unsustainable to the NHS.<https://news.sky.com/story/record-rise-in-babies-born-with-brain-damage-sees-nhs-compensation-bill-soar-10991025>. The UK Government has recently (October 2016) announced that reducing birth asphyxia related costs is a priority area for the Government. <https://www.gov.uk/government/news/improving-the-safety-of-maternity-care-in-the-nhs>

The only effective treatment for HIE is whole body cooling, with an estimated saving of £100 million per annum³ to the UK economy, since its introduction as a standard therapy in the NHS in 2007. Cooling therapy has substantially improved the outcomes of babies with HIE in the past decade. However, unacceptably high rate of adverse outcomes are still seen in cooled babies with moderate or severe HIE: death 28% (range 24–38); cognitive impairment 24% (range 21–25); cerebral palsy 22% (range 13–28); epilepsy 19% (range 15–24); cortical visual impairment 6% (range 1–10), with combined death or moderate/severe disability 48% (range 44–53)⁴, and hence better treatments and further optimisation of cooling therapy is required.

A key roadblock in clinical translation of over 15 highly effective neuroprotective treatments in animal models⁵ is the long delay between the intervention and outcome assessments in HIE. i.e. the earliest age at which neurodevelopmental outcome can be accurately assessed is 18 months. Hence, despite having over 2 dozen highly effective treatments in animal models, no further neuroprotective drugs in HIE have been introduced into the NHS in the past 10 years.

Magnetic resonance biomarkers to accelerate clinical translation

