7. STATISTICS AND DATA ANALYSIS

We expect to recruit at least 60% of the eligible population and to have adequate quality data on the primary outcome for the main trial (i.e. thalamic N-acetylaspartate concentration) in >95% of the recruited babies.

We will use an unpaired t-test to estimate the difference in thalamic/basal ganglia NAA concentration between infants receiving erythropoietin and Darbepoetin alfa.

The standard deviation of [NAA] in the MARBLE study was 0.8. To detect a difference of 0.5 mmol/kg wet weight of [NAA] at 90% power and 0.017 significance, 71 infants will be required for each of the 3 groups for unadjusted analysis. The total sample size is increased to 220 to account for neonatal mortality and any unusable data due to motion artefacts. Data and all appropriate documentation will be stored for a minimum of 10 years after the completion of the study, including the follow-up period.

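### The increase from 213 to 220 covers only 3.2% loss for deaths and unusable scans together, so the stated 90% power is not supported once total loss passes about 4%

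*Protocol*

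**What the plan says.** Protocol section 7 builds the sample size in three steps.

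- Inputs: "The standard deviation of [NAA] in the MARBLE study was 0.8", and "To detect a difference of 0.5 mmol/kg wet weight of [NAA] at 90% power and 0.017 significance".
- Result: "71 infants will be required for each of the 3 groups for unadjusted analysis".
- Inflation: "The total sample size is increased to 220 to account for neonatal mortality and any unusable data due to motion artefacts".

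The section opens with an expectation of adequate quality data on "thalamic N-acetylaspartate concentration) in >95% of the recruited babies". It gives no separate rate for deaths before the scan or for spectra lost to motion.

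Two other places bear on the allowance. The design section puts the MR scan at 1 to 2 weeks after birth. Section 1.1 says "unacceptably high rate of adverse outcomes are still seen in cooled babies with moderate or severe HIE: death 28" (per cent, with a range of 24 to 38) and gives no age at which those deaths were counted.

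**The concern.** The primary outcome is measured only in a baby who is alive at 1 to 2 weeks and whose spectrum can be quantified. Every earlier death and every unusable scan removes an observation from the comparison. The inflation therefore has to cover both losses, and 7 babies is very few for a condition whose mortality the protocol itself describes as high.

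The 90% power is the justification given for the size of the trial. Section 1.1 also says the study will provide a go or no-go signal for a later placebo-controlled trial. If fewer babies are evaluable than planned, a comparison that finds no difference is weaker evidence than the stated power suggests, and the protocol gives a reader no means of judging by how much.

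**Working it through.** **Inputs.** SD 0.8, difference 0.5 mmol/kg wet weight, significance 0.017, power 90%, 71 per group and a total of 220, all from section 7. Assumptions: a two-sided test, 1:1:1 allocation and equal loss across arms. The protocol states none of these, but the first two fit its figures.

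**Step 1: reproduce 71 per group.**

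Normal approximation: n = 2 × (z for 1 − 0.017/2 + z for 0.90)² × SD² / difference² = 2 × (2.387 + 1.282)² × 0.64 / 0.25 = 68.9, so 69.

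Exact two-sided unpaired t-test (noncentral t): power is 89.8% at 70 per group and 90.3% at 71. So 71 is the smallest number that reaches 90%, and the protocol's figure reproduces. A one-sided test would need only 60 by the normal approximation, so the figure is two-sided.

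**Step 2: the allowance.** 71 × 3 = 213; 220 − 213 = 7; 7/220 = 3.2%.

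**Step 3: against the section's own expectation.** A 5% loss is the limit of what the 95% expectation tolerates. 220 × 0.95 = 209, which is 4 short of 213. Holding 213 at that loss would take 213/0.95 = 224.2, so 225. The effect on power is small: 209/3 = 69.7 per group gives 89.7%.

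**Step 4: power at 220 randomised, by total loss d from any cause.** Evaluable per group = 220 × (1 − d)/3, with the same t-test. The last column is the difference detectable with 90% power.

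| Total loss | Evaluable | Per group | Power for 0.5 | Detectable at 90% |
|---|---|---|---|---|
| 3.2% | 213 | 71.0 | 90.3% | 0.50 |
| 5% | 209 | 69.7 | 89.7% | 0.50 |
| 10% | 198 | 66.0 | 87.8% | 0.52 |
| 14% | 189 | 63.1 | 86.0% | 0.53 |
| 20% | 176 | 58.7 | 83.1% | 0.55 |
| 28% | 158 | 52.8 | 78.2% | 0.58 |

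Power falls below 90% at a total loss of about 4.1%. That is slightly above 3.2% because rounding up to 71 gives 90.3%. It falls below 88% at about 9.5%.

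The losses in this table are an assumed range, since the protocol gives no pre-scan death rate. The 14% row is half of 28%. The 28% row is the case in which every death behind the quoted figure precedes the scan and no scan fails.

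**The case against.** The strongest reply has four parts.

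1. **The 28% is not pre-scan mortality.** It has no time point. It is listed beside cognitive impairment, cerebral palsy, epilepsy and combined death or disability, and section 1.1 says neurodevelopment cannot be accurately assessed before 18 months. It therefore reads as mortality over follow-up. It also describes moderate or severe HIE, whereas section 4.1 admits mild cases (the design section excludes them, and the two are not reconciled). This stands. A reader might set 3.2% against 28% and infer that the trial is badly underpowered. The protocol does not support that: for the population it describes, 28% can serve only as an upper case.

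2. **The 95% expectation has recruited babies as its denominator.** Read literally, it already counts deaths. Treating it as a 5% scan-failure rate and adding deaths on top would count some losses twice. Further, 213/220 = 96.8%, so a total of 220 and the 95% expectation are compatible, and even at exactly 95% power is 89.7%. This stands too. It does not show that deaths and failed scans together will stay below 5%; no figure in the protocol supports that.

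3. **Other evidence in the protocol points to few early deaths.** Appendix 1 lists a series of 24 cooled, erythropoietin-treated infants with no neonatal deaths, and one of 9 infants with severe HIE and none. These are small, treated and uncontrolled. Even pooled, 0 of 33 has a one-sided 95% upper limit of 1 − 0.05^(1/33) = 8.7%, well above the 3.2% allowance. They temper the concern without settling it.

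4. **This is called a pilot, and the loss of power is modest at plausible rates.** At 10% total loss, power is 87.8% and the detectable difference moves from 0.50 to 0.52. That is fair. Nor does the protocol tie its go or no-go signal to a significance test. But it chose to justify its size by 90% power, so that figure should rest on stated losses.

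**Conclusion.** The point holds as a matter of an unsupported allowance. The derivation of 71 per group is correct; the step from 213 to 220 is not justified by anything in the protocol. It covers 3.2% for two causes of loss, which is less than the 5% the same section tolerates and hard to reconcile with the only mortality rate it quotes for cooled moderate or severe HIE.

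A reader might conclude that the 90% power will not be achieved. The protocol does not establish that, because it gives no pre-scan death rate. The conclusion is conditional: 90% is lost once total loss exceeds about 4%, negligibly so at 5% (89.7%), modestly at 10% to 14% (87.8% to 86.0%), and materially at 20% to 28% (83.1% to 78.2%). These figures assume SD 0.8, a two-sided test at 0.017, equal allocation and equal loss across arms.

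**What to change.** Keep 220 and change the wording of section 7.

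- State the expected proportion of babies dying before the scan and the expected proportion of scans with unusable spectra as two separate figures, each with its basis.
- Reconcile them with the 95% expectation, and say whether its denominator is babies recruited or babies scanned.
- Replace the 90% with the result for the evaluable number per arm that follows. For example: *Assuming x% death before MR and y% unusable spectra among those scanned, 220 randomised gives about n evaluable per arm, with p% power to detect 0.5 mmol/kg, or 90% power to detect z mmol/kg.* A short table like the one above would cover uncertainty in x and y.

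The cost is wording and a slightly less favourable stated power. No extra babies are needed, and neither the significance level nor the planned comparisons change.

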8. REGULATORY ISSUES

8.1 ETHICS APPROVAL

The Study Coordination Centre has obtained approval from the West of Scotland Research Ethics Committee (REC) and Health Regulator Authority (HRA). The study must also receive confirmation of capacity and capability from each participating NHS Trust before accepting participants into the study or any research activity is carried out. The study will be conducted in accordance with the recommendations for physicians involved in research on human subjects adopted by the 18th World Medical Assembly, Helsinki 1964 and later revisions.

8.2 CONSENT

8.2.1 Phase 1:

Consent to enter the study must be sought from each participant only after a full explanation has been given, an information leaflet offered, and time allowed for consideration. Signed participant consent should be obtained. The right of the participant to refuse to participate without giving reasons must be respected. All participants are free to withdraw at any time from the protocol treatment without giving reasons and without prejudicing further treatment.

8.2.2 Phase 2:

Informed parental consent will be obtained prior to recruitment and randomisation but since the study requires data collection as soon as possible after birth, only the blood collection may begin before informed parental consent is obtained (deferred consenting) at the same time as the clinical blood sample collection on admission.

Parents will be informed about the study at the earliest appropriate opportunity (within 12 hours of birth) and will be given the Parent Information leaflet (PIL). Parents wishing to participate in the study will be asked to sign an informed consent form and be given a copy for their records (with the PIL), their baby will be randomised into one of the three groups only after parental consent. If the parents do not wish to participate in the study, data collection will be interrupted, and the blood samples obtained up to that point will be discarded.

Whether or not the parent(s) decide to take part in the study shall not affect the clinical decisions made during the care of the baby, nor the quality of care provided. All participants are free to withdraw from the study at any time without giving any reason and without prejudicing further treatment.

8.3 CONFIDENTIALITY

The Chief Investigator will preserve the confidentiality of participants taking part in the study and is registered under the Data Protection Act.

8.4 INDEMNITY

Imperial College London holds negligent harm and non-negligent harm insurance policies which apply to this study.

8.5 SPONSOR

Imperial College London will act as the main Sponsor for this study. Delegated responsibilities will be assigned to the NHS trusts taking part in this study.

8.6 FUNDING

National Institute for Health Research and Garfield Weston Foundation, Imperial College London are funding this study.

8.7 AUDITS

The study may be subject to inspection and audit by Imperial College London under their remit as sponsor and other regulatory bodies to ensure adherence to GCP and the UK Policy Framework for Health and Social Care Research.

9. STUDY MANAGEMENT

A Trial Management Group (TMG) will be appointed and will be responsible for overseeing the progress of the trial. The day-to-day management of the trial will be co-ordinated through the Study Coordination Centre. An independent Data Monitoring Committee will be appointed.

10. PUBLICATION POLICY

All publications and presentations relating to the study will be authorised by the Trial Management Group. The first publication of the trial results will be in the name of the Trial Management Group, if this does not conflict with the journal's policy. If there are named authors, these will include at least the trial's Chief Investigator, Statistician and Trial Coordinator. Members of the TMG and the Data Monitoring Committee will be listed, and contributors will be cited by name if published in a journal where this does not conflict with the journal's policy. Authorship of parallel studies initiated outside of the Trial Management Group will be according to the individuals involved in the project but must acknowledge the contribution of the Trial Management Group and the Study Coordination Centre.

12. APPENDICES

APPENDIX 1: Summary of clinical studies on ESAs on term infants with NE.

Author/Paper	Population	Dose	Route	Key Results/Safety

		total of 5 doses		The incidence of adverse outcomes was similar between the two groups. Hypotension, hepatic dysfunction, prolonged coagulation and necrotizing enterocolitis were similar between the two groups. Although red blood cell indices (haemoglobin, red blood cell count and reticulocyte count) were elevated in the treatment group on day 10 of life, these normalized by 1 month of age and no complications were seen. There were no patients with hypertension, polycythaemia or thrombosis secondary to EPO.

		4 doses, and 1 infant 5 doses)		
Wang, S.Y. Effect of mild hypothermia combined with Vit C and EPO therapy on target organ damage in children with neonatal asphyxia. J. Hainan Med. Univ. 2017 , 23, 117–120.	68 infants (37-40 weeks' gestation) with HIE, 2 groups, moderate hypothermia, EPO & Vitamin C ($n = 34$), EPO & Vitamin C ($n = 34$)	500 U/kg 3 doses/week	i.v. for EPO and Vitamin C (250 mg/kg)	Mild hypothermia, EPO & Vitamin C combined more effective. This was achieved through decreased apoptosis and oxygen free radicals, and increased antioxidant capacity
